15.3.2 Serious Adverse Events

Population: SAF analysis set

SAEs will be summarized for each dose level and overall, by SOC and PT in alphabetical order, as described at section 15.2.1.

In addition, subject listings of SAEs will be provided (refer to section 15.2.1 for items to be listed).

15.4 Clinical Laboratory Evaluation

Population: SAF analysis set

Local laboratory values captured on the "Hematology" and "Biochemistry" eCRF pages will be used for summary statistics and shift tables.

Laboratory results (including corresponding normal ranges) will be classified according to the NCI-CTCAE version 4.03 and distinguished between Common Terminology Criteria (CTC) gradable and non-CTC gradable parameters.

Common Terminology Criteria (CTC) gradable parameters

In this trial, CTC gradable parameters are the following:

Category Parameter (LBTEST) Parameter code (LBTESTCD)		Name in NCI-CTC	Direction of abnormality	
	Biochemistry			
Electrolytes	Calcium	CA	Hypocalcemia/Hypercalcemia	Low/High
Electrolytes	Magnesium	MG	Hypomagnesemia/Hypermagnesemia	Low/High
Electrolytes	Phosphorus (Phosphate)	PHOS	Hypophosphatemia	Low
Electrolytes	Potassium	K	Hypokalemia/Hyperkalemia	Low/High
Electrolytes	Sodium	SODIUM	Hyponatremia/Hypernatremia	Low/High
Enzymes/cardiac	Creatinine Phosphokinase	CK	CPK increased	High
Enzymes/liver	Alanine Aminotransferase	ALT	Alanine Aminotransferase increased	High
Enzymes/liver	Alkaline Phosphatase	ALP	Alkaline Phosphatase increased	High
Enzymes/liver	Aspartate Aminotransferase	AST	Aspartate Aminotransferase increased	High
Enzymes/liver	Gamma-glutamyltransferase	GGT	GGT increased	High
Enzymes/liver	Total bilirubin	BILI	Blood bilirubin increased	High
Enzymes/pancreas	Lipase	LIPASET	Lipase increased	High
Enzymes/pancreas	Serum amylase	AMYLASE	Serum amylase increased	High
Metabolism	Glucose	GLUC	Hypoglycemia/Hyperglycemia	Low/High
Metabolism	Uric acid ⁽¹⁾	URATE	Hyperuricemia	High
Plasma proteins	Albumin	ALB	Hypoalbuminemia	Low
Renal/kidney	Creatinine	CREAT	Creatinine increased	High
Renal/kidney	Creatinine Clearance	CREATCLR	part of Chronic kidney disease	Low
	Hematology			
Platelets	Platelets Count	PLAT	Platelet count decreased	Low
Red blood cells	Hemoglobin	HGB	Anemia/Hemoglobin increased	Low/High

Category	Parameter (LBTEST)	Parameter code (LBTESTCD)	Name in NCI-CTC	Direction of abnormality
White blood cells/differential	White Blood Cell Count	WBC	White blood cell decreased/Leukocytosis	Low/High
White blood cells/differential	Absolute Lymphocytes Count	LYM	Lymphocyte count decreased/increased	Low/High
White blood cells/differential	Absolute Neutrophils Count	NEUT	Neutrophil count decreased	Low

- (1) According to CTCAE grade, if uric acid value is between ULN and 590 μmol/L it should be graded as following:
 - Grade 1 if there are no physiologic consequences
 - Grade 3 if there are physiologic consequences

For a programming perspective, values between ULN and 590 μ mol/L will all be graded as Grade 1 (if any physiologic consequences are observed, it should be completed as an adverse event).

For all CTC gradable parameters, shift tables from baseline to worst grade during the on-treatment period (as defined in section 9) will be produced. The worst grade per subject will be defined as the highest CTC grade among the on-treatment evaluations. If there is no on-treatment evaluation, then the worst grade will be set to 'Missing'. Parameters will be grouped by category.

Non-CTC gradable parameters

In this trial, non-CTC gradable parameters are displayed in table below:

Category	Parameter (LBTEST)	Parameter code	Direction of
		(LBTESTCD)	abnormality
	Biochemistry		
Electrolytes	Chloride	CL	High/Low
Enzymes/cardiac	Lactate dehydrogenase	LDH	High
Enzymes/liver	Direct bilirubin	BILDIR	High
Plasma proteins	Total protein	PROT	Low
Renal/kidney	Blood Urea Nitrogen	UREANUREAN	High
Renal/kidney	Urea	UREA	High
	Hematology		
Red blood cells	Red blood cells (Erythrocytes)	RBC	High/Low
Red blood cells	Reticulocytes/Erythrocytes	RETIRBC	High/Low
Red blood cells	Reticulocytes	RETI	High/Low
White blood cells/differential	Lymphocytes/Leukocytes	LYMLE	High/Low
White blood cells/differential	Neutrophils/Leukocytes	NEUTLE	High/Low
White blood cells/differential	Basophils/Leukocytes	BASOLE	High
White blood cells/differential	Basophils	BASO	High
White blood cells/differential	Eosinophils/Leukocytes	EOSLE	High
White blood cells/differential	Eosinophils	EOS	High
White blood cells/differential	Monocytes/Leukocytes	MONOLE	High/Low
White blood cells/differential	Monocytes	MONO	High/Low

Shift tables based on the normal range from baseline (as defined in section 9) to worst on-treatment value will be produced with the following categories for all hematology and blood chemistry parameters (CTC gradable and non-CTC gradable):

- Baseline: Low/Normal/High/Missing/Total
- Worst On-treatment: Low/Normal/High/Missing/Total

Normal category includes low values for high parameters and high values for low parameters.

Only subjects with post baseline laboratory values will be included in these analyses.

In addition, a spider graph to investigate the evolution in time of some specific hematology and biochemistry parameters will display the observed value against thetreatment day. One graph per dose level will be produced for the following parameters:

- Hematology: all parameters within "White blood cells/differential" category
- Biochemistry: AST, ALT and Albumin

All CTC gradable and non-CTC gradable parameters will be listed for each measurement (pretreatment, on-treatment and post-treatment). Parameters will be grouped by category.

Listings will include at least the following items:

- Dose Level
- Subject ID
- First / last M3541 / RT administration date and number of fraction days
- Age, sex and race
- Category
- Parameter (SI unit)
- Visit
- Date of collection (relative day)
- Observed value
- Change from baseline
- Reference range and normal range indicator (Low, Normal, High)
- NCI CTCAE grade
- Baseline flag
- Worst value on-treatment flag (Min/Max)

In addition, a listing displaying parameters with at least one value with grade ≥ 3 will be provided. For each subject, only parameters where at least one value has grade ≥ 3 will be displayed (all visits for the corresponding parameter will be displayed).

Coagulation parameters

All coagulation parameters captured on the "Coagulation" eCRF page will be listed for each measurement (pre-treatment, on-treatment and post-treatment).

Urinalysis

A listing of urinalysis and microscopic analysis captured on the "Urinalysis" and "Urinalysis Microscopic Evaluation" eCRF pages will be provided.

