AE = adverse event; β-HCG = beta-human chorionic gonadotropin; BPI-SF = Brief Pain Inventory – Short Form; CT = computed tomography; ctDNA = circulating tumor DNA; DLT = dose-limiting toxicity; ECG = electrocardiogram; ECOG PS = Eastern Cooperative Oncology Group performance status; eCRF = electronic case report form; EoS = End-of-Study; FD = Fraction Day (days when RT and M3541 are given); FU = follow-up; Gy = Gray; HBV = hepatitis B virus; HCV = hepatitis C virus; HIV = human immunodeficiency virus; MRI = magnetic resonance imaging; PK = pharmacokinetics; PTD = Post-treatment Day (starting the day after the last dose of RT and M3541 until 1 year later); QTCF = Fridericia corrected QT interval; RECIST 1.1 = Response Evaluation Criteria in Solid Tumors version 1.1; RT = radiotherapy; TEAE = treatment-emergent adverse event.

Note: Where scheduled post-treatment visits coincide with a weekend or holiday, they may be postponed to the next working day (up to + 2 days). The relevance of any safety finding during this additional time in the context of a DLT or any other late toxicity will be reviewed by the Safety Monitoring Committee.

- a. All subjects will be followed up for disease progression until 1 year after RT is completed, or earlier due to any reason whereby tumor assessments are no longer applicable (eg, PD, if a new treatment is started, withdrawal of consent). The reason for early discontinuation should be captured in the source document. If EoS occurs prior to PTD 365, all assessments must be done as planned for PTD 365. All subjects will be followed for survival and for delayed AEs for up to 1 year (and beyond for AEs) from PTD1. After the 1 year follow-up, the Investigator will be asked to contact subjects every 3 months (± 1 month, phone call is acceptable) until the defined end of the study (see Section 5.7) to enquire and monitor for late appearing RT-related toxicity.

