#### 8.5.1 General Considerations

All data recorded during the study will be presented in individual data listings performed on the Safety Analysis Set. All data will be evaluated as observed, and no imputation method for missing values will be used unless otherwise specified in the SAP. All data will be presented in a descriptive manner. Each cohort will be analyzed separately, and no multiplicity adjustment across cohorts will be performed.

Descriptive statistics will be used to summarize the study results, that is, statistics for continuous variables may include means, medians, ranges, and appropriate measures of variability. Qualitative variables will be summarized by counts and percentages. The uncertainty of estimates will be assessed by confidence intervals. Unless otherwise specified, the calculation of proportions will be based on the sample size of the analysis set of interest. Counts of missing observations will be included in the denominator and presented as a separate category if not otherwise specified in the SAP.

The DLT Analysis Set is the underlying data set for the MTD determination. Safety analyses will be performed on the Safety Analysis Set. Baseline summaries and efficacy analyses will be performed on the Safety Analysis Set. Analyses of PK variables will be performed on the PK Analysis Set. Analyses of biomarkers will be performed on the respective Biomarker Analysis Sets.

Posterior distribution and recommended next dose level will be calculated using EAST Version 6.4 or higher. The estimation of PK parameters will be performed using WinNonlin® Version 6.4 or higher. All other statistical analyses will be performed using SAS® Version 9.2 or higher, or R, Version 3.0.2 or higher.

Data cut-off for the primary analyses is defined by the completion of DLT evaluation period of the last subject in the last cohort.

The final analysis will be performed when the study has been completed (see Section 5.7).

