9 General Specifications for Data Analyses

Posterior distribution and recommended next dose level will be calculated using EAST Version 6.4 or higher.

Non-compartmental computation of PK parameters will be performed using Phoenix WinNonlin Version 6.4, or higher.

All other statistical analyses will be performed using SAS Version 9.2 or higher, or R, Version 3.0.2 or higher.

Pharmacokinetic figures will be prepared using SigmaPlot Version 12.5 or higher or SAS Version 9.2 or higher.

Data handling after cut-off date for SMC and primary analyses:

Data after cut-off for SMC and primary analyses do not undergo the cleaning process. Hence data obtained after the cut-off will not be displayed in listings or used for summary statistics (e.g. laboratory values of samples taken after data cut-off, AE with onset date after data cut-off, etc.).

Presentation of continuous and qualitative variables:

Data will be presented by dose level and overall unless specified otherwise. The dose level will be defined by the planned dose of the corresponding cohort. If several cohorts have same dose level, they will be pooled together for all summary outputs.

Continuous variables will be summarized using descriptive statistics, i.e.

• Number and percentage of subjects, number and percentage of subjects with missing values

- Mean, 95% confidence intervals (CI), as appropriate
- Standard deviation (SD)
- Median
- Q1, and Q3
- Minimum (Min), and maximum (Max)

Mean, median, Q1, Q3, Min, and Max will have the same precision as collected in SDTM datasets for non-derived data. Standard deviation will be presented with 1 digit more than the mean. For derived data, the number of decimal digits will be defined on a case-by-case basis.

Missing statistics, e.g., when they cannot be calculated, should be presented as "nd". For example, if n=1, the standard deviation cannot be computed and should be presented as "nd".

Qualitative variables will be summarized by frequencies and percentages.

Unless otherwise stated, the calculation of proportions will be based on the number of subjects of the analysis set of interest. Therefore, counts of missing observations will be included in the denominator and presented as a separate category.

If there are no missing values, this should be indicated by a 0 (0.0).

In case the analysis refers only to certain visits, percentages will be based on the number of subjects still present in the trial at that visit, unless otherwise specified.

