Presentation of pharmacokinetic/biomarker concentration data

Pharmacokinetic/biomarker concentration data will be descriptively summarized per dose level using: number of non-missing observations (N), arithmetic mean (Mean), SD, coefficient of variation (CV%), Min, median, and Max.

Descriptive statistics of PK/biomarker concentration data will be calculated using values with the same precision as the source data, and rounded for reporting purposes only. The following conventions will be applied when reporting descriptive statistics of PK/biomarker concentration data:

Mean, Min, Median, Max: 3 significant digits

SD: 4 significant digits

CV%: 1 decimal place

Presentation of pharmacokinetic parameter data

Pharmacokinetic parameter data will be descriptively summarized per dose level using: N, Mean, SD, CV%, Min, Median, Max, geometric mean (GeoMean), and the geometric coefficient of

variation (GeoCV) and the 95% CI for the GeoMean (lower CILCI 95% GeoMean, Upper CIGM, UCI 95% GeoMean).GM)

The following conventions will be applied when reporting descriptive statistics of PK parameter data:

Mean, Min, Median, Max, GeoMean, 95% CI: 3 significant digits

SD: 4 significant digits

CV%, GeoCV%: 1 decimal place

Definition of baseline:

The last non-missing measurement prior to first administration of M3541 will be used as the baseline measurement.

Definition of treatment day:

Treatment day 1 is defined as the date of first administration of M3541, the day before is defined as Treatment day –1 (no Treatment day 0 is defined).

Definition of fraction day:

Fraction days are defined as days of radiotherapy administration.

Definition of on-treatment period for safety analyses:

On-treatment period for safety analyses will be the time from the Treatment day 1 until the last M3541 administration date + 30 days (PTD 30), the earliest date of subsequent anticancer drug therapy minus 1 day or the clinical cut-off date (if the treatment is still ongoing), whichever occurs first.

Subsequent anticancer drug therapy date will be based on "Anti-cancer treatment after discontinuation", "Radiotherapy after discontinuation", and "Surgery after discontinuation" eCRF pages.

Definition of duration:

Duration will be calculated by the difference of start and stop date + 1 (e.g. survival time (days) = date of death – date of first dose + 1), if not otherwise specified.

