The time since an event (e.g. time since first diagnosis) will be calculated as reference date minus date of event.

Definition of DLT evaluation period:

For all subjects enrolled before protocol v5.0 (amendment 4.0):

The DLT evaluation period will start on the day of the first administration of M3541 / RT and will end 23 days after the last administration of M3541 / RT (2-day M3541 / RT holiday after the last fraction day (FD) plus a 3-week DLT follow-up period that starts on the third day after the last administration of M3541 / RT). The end date of the period will be calculated as follows:

Date of last administration of M3541/RT + 23 days

The DLT evaluation period will be 5 weeks in duration, unless M3541 / RT has been interrupted for up to 3 days.

For all subjects enrolled under or after protocol v5.0 (amendment 4.0):

The DLT evaluation period will start on the day of the first administration of M3541 / RT and will end 14 days after the last administration of M3541 / RT (2-week radiotherapy treatment period plus a 2-week DLT follow-up period that starts on the day after the last administration of M3541 / RT). The end date of the period will be calculated as follows:

Date of last administration of M3541/RT + 14 days

The DLT evaluation period will be 4 weeks in duration, unless M3541 / RT has been interrupted and given over a period exceeding 2 weeks.

Definition of analysis time points

Actual time elapsed from first M3541 administration in hours will be derived as:

$$Actual\ time\ (hours) = \frac{Datetime\ of\ interest - Datetime\ first\ M3541\ dose}{3600}$$

Nominal time elapsed from first M3541 administration in hours will be derived according to the following rules:

- For results collected at screening, Nominal time = -1
- For results collected from fraction day 1 to fraction day 5:

Nominal time Nominal time =
$$(X - 1) * 24 + Y$$

• For results collected from fraction day 6 to fraction day 10:

Nominal time Nominal time =
$$(X + 1) * 24 + Y$$

With X = fraction day and Y = number of hours elapsed from M3541 administration on X. Y = 0 for predose samples.

Of note, the nominal time will not be derived for unscheduled samples.

The time points at which assessments are expected are reported below (distinguishing among subjects enrolled before protocol v5.0 (EARLY) and under it (LATE)):

Table 4: Nominal time points for ECG, pharmacodynamics and immune system sampling

X	Y	Nominal Time from first M3541 dose (in hours)	ECG		ECG		ECG PD		IM	

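### The SAP ends the laboratory window at last M3541 + 30 days, which is not PTD 30 for pre-v5.0 subjects, so post-treatment lab ascertainment differs by protocol version, a factor largely confounded with dose

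*SAP*

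**What the plan says.** **Tables.** SAP 15.4 says of CTC-gradable parameters that "shift tables from baseline to worst grade during the on-treatment period (as defined in section 9) will be produced". The value entered in these tables is a maximum over draws, in the SAP's words: "The worst grade per subject will be defined as the highest CTC grade among the on-treatment evaluations". It also plans normal-range shift tables, baseline to worst on-treatment value, for all hematology and chemistry parameters. The default layout is in SAP section 9: "Data will be presented by dose level and overall unless specified otherwise". Section 15.4 does not override it.

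**Window.** SAP section 9 opens the on-treatment period with the first M3541 dose. Its end is given as "until the last M3541 administration date + 30 days (PTD 30), the earliest date of subsequent anticancer drug therapy minus 1 day". A data cut-off can also close it, and the first of these dates applies.

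**Day numbering.** Under its DLT evaluation period heading, SAP section 9 describes, for subjects enrolled before v5.0, "a 3-week DLT follow-up period that starts on the third day after the last administration of M3541 / RT". For v5.0 subjects the follow-up starts on the next day.

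**Visits.** Protocol 7.1.3 and 7.1.4 place v5.0 visits at PTD 15 (+2 days), PTD 22 (±2) and PTD 30 (±2). The Table 1 note lets a weekend visit slide up to two days to the next working day. The marked-up Table 1 in Appendix V shows what earlier subjects followed: post-treatment labs at PTD 22 and PTD 30 only. The in-treatment lab days were not changed.

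**Version handling.** SAP section 9 separates pre-v5.0 from v5.0 subjects for the DLT period and, in its Table 4, for ECG, pharmacodynamic and immune samples. It makes no such split for laboratory data.

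**The concern.** A subject's worst grade is a maximum, so an extra draw can leave it unchanged or raise it but never lower it. If one protocol version contributes more counted draws than the other, the tables are not like for like. Version also tracks dose: the 50 mg and 100 mg subjects reported in Protocol 3.1.5 predate v5.0. A reader who scans the shift tables by dose level could take a difference in sampling for a difference in tolerability.

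Separately, a safety lab set that the protocol schedules drops out of the summary tables because a day count and a visit label that the SAP treats as equal are not equal for the earlier subjects. The post-treatment period matters here. Protocol 3.1.5 reports a half-life above 48 hours with accumulation, and Protocol 6.5.4 names blood-forming tissue, liver, kidneys and pancreas among the target organs.

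**Working it through.** **1. Reproduce the SAP's own figures.** Before v5.0, PTD 1 is last dose + 3, so PTD k = +(k + 2). Then PTD 21 = +23, the SAP's end of the DLT period. Under v5.0, PTD k = +k, so PTD 14 = +14, again the SAP's figure. The numbering is confirmed.

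**2. Apply it to the cut.** Last dose + 30 is PTD 30 under v5.0 but PTD 28 (30 − 2) before v5.0. The pre-v5.0 PTD 30 visit is at +32.

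**3. Place the visits on a calendar.** Assume that the last M3541 dose and last RT fraction fall together on a Friday (day 0).

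| Version | Visit | Nominal day | Window | Working days in window | Inside the +30 cut? |
|---|---|---|---|---|---|
| pre-v5.0 | PTD 22 | +24 Mon | +22 to +26 | Mon +24 to Wed +26 | yes |
| pre-v5.0 | PTD 30 | +32 Tue | +30 to +34 | Mon +31 to Thu +34 | none (only Sunday +30) |
| v5.0 | PTD 15 | +15 Sat | +15 to +17 | Mon +17 | yes |
| v5.0 | PTD 22 | +22 Sat | +20 to +24 | Thu +20, Fri +21, Mon +24 | yes |
| v5.0 | PTD 30 | +30 Sun | +28 to +32 | Fri +28, Mon +31, Tue +32 | Friday only |

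**4. Count the draws.** Scheduled post-treatment draws counted: 1 before v5.0, and 2 or 3 under v5.0 if no new therapy intervenes. Both versions share five post-baseline in-treatment draws: FD 3, 5, 6, 8 and 10, the last taken on FD 9 when FD 10 is a Friday. Totals are 5 + 1 = 6 against 5 + 2 = 7 or 5 + 3 = 8.

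**5. Effect on the whole table.** Let p be an assumed probability that a single draw reaches a given grade. For n independent draws, P(at least one) = 1 − (1 − p)^n.

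| p | 6 draws | 7 to 8 draws | Difference (points) |
|---|---|---|---|
| 0.02 | 11.4% | 13.2-14.9% | 1.8-3.5 |
| 0.05 | 26.5% | 30.2-33.7% | 3.7-7.2 |
| 0.10 | 46.9% | 52.2-57.0% | 5.3-10.1 |

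Draws within a subject are correlated. In a Gaussian-copula simulation at p = 0.05, latent correlation 0.5 gives 18.7% against 20.5-22.0%, and 0.8 gives 12.7% against 13.5-14.1%.

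**6. Effect on abnormalities that arise after treatment.** For a toxicity seen only then, with p = 0.05 and independent draws, 1 draw gives 5.0%, against 9.8% (2 draws) to 14.3% (3 draws). As an alternative, assume a silent episode with onset uniform on days +1 to +30, found if a draw falls inside it.

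| Episode length | Draw at +24 (pre-v5.0) | Draws at +17, +24 (v5.0) | Draws at +17, +21, +28 (v5.0) |
|---|---|---|---|
| 7 days | 7/30 = 23% | 14/30 = 47% | 18/30 = 60% |
| 14 days | 14/30 = 47% | 21/30 = 70% | 25/30 = 83% |

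**7. Version against dose.** Protocol 3.1.5 reports 3 subjects at 50 mg, 4 at 100 mg and 1 at 200 mg when Amendment 4 was submitted. Any further 200 mg enrolment under v5.0 makes that level mixed. The documents do not say how many subjects followed at any dose.

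**8. What each remedy does.** Counting PTD 30 by visit gives 2 draws (PTD 22, 30) against 3 (PTD 15, 22, 30). Restricting to in-treatment draws gives 5 against 5.

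**The case against.** Several counter-arguments have force.

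- **The window follows the protocol.** Protocol 8.5.4.1 also sets last administration + 30 days and calls it PTD 30. That stands, but the equation is true only under v5.0 numbering. The section defines treatment-emergent adverse events; for labs, Protocol 8.5.4.2 asks for the worst on-study grade and states no 30-day limit.
- **The values are not lost.** SAP 15.4 lists every measurement, including post-treatment ones, with relative day. It shows all visits for any parameter that reaches grade 3, and it plots the white-cell parameters, AST, ALT and albumin over time. This stands: the gap is confined to the shift tables.
- **The analysis is descriptive.** Protocol 8.5.1 says: "All data will be presented in a descriptive manner". MTD determination uses the DLT Analysis Set, and no passage ties these tables to the RP2D. This stands.
- **The v5.0 count is an upper bound.** Amendment 4 lets subjects start their next therapy sooner, which closes the window the day before. SAP section 9 also takes that date from the post-treatment radiotherapy and surgery pages, and Protocol 6.5.2 permits radiotherapy to other lesions beyond PTD 7. The gap could narrow or reverse. This is correct, and it is a further ascertainment difference between versions. Unscheduled draws also count for everyone.
- **The course may slip.** Up to 3 FDs of delay are allowed. If FD 10 moves to Monday, Tuesday or Wednesday, day +30 is a Wednesday, Thursday or Friday, so a PTD 30 visit can fall inside the cut. The exclusion is therefore the usual case, not a universal one.

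A reader might infer that laboratory toxicity must rise with dose by construction. The documents do not support that. The 50 mg and 100 mg subjects reported at Amendment 4 share one schedule, and all v5.0 subjects share another. The artefact is one step at the version change.

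**Conclusion.** The point holds in a limited form. SAP section 9 treats last M3541 + 30 days and PTD 30 as the same for everyone, which is wrong by two days for pre-v5.0 subjects. On the planned calendar, their PTD 30 labs, and v5.0 PTD 30 labs taken on Monday, are left out of the SAP 15.4 shift tables. Post-treatment ascertainment is then 1 scheduled draw against 2 or 3.

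The overall effect is modest. At p = 0.05 it is 3.7 to 7.2 points if draws are independent, and about 1 to 3 points at latent correlations of 0.8 and 0.5. With 3 to 4 subjects at a dose level, even the independent case is about 0.1 to 0.3 of a subject (3 × 0.037 to 4 × 0.072). The effect matters mainly for abnormalities that arise after treatment, where the chance of detection can double or more under the stated assumptions.

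These sizes rest on assumed values of p, correlation, episode length and onset, on an uninterrupted Friday finish, and on no early new therapy. Confounding with dose is clear for the 50 mg and 100 mg subjects reported at Amendment 4. Above that it depends on enrolment that the documents do not report.

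**What to change.** In SAP sections 9 and 15.4, for the laboratory shift tables only:

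1. Count PTD 30 visit labs as on-treatment by visit: up to last M3541/RT + 34 days for pre-v5.0 subjects and + 32 days for v5.0 subjects, still ending at new anticancer therapy. State that + 30 days is PTD 28 in the earlier numbering.
2. Because this alone leaves 2 against 3 draws, add a worst-grade shift table restricted to the FD 1 to FD 10 draws, which follow the same schedule in both versions.
3. Show post-treatment worst grade by protocol version.

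The cost is SAP wording, a slightly longer laboratory window that differs by two days between versions, one extra descriptive table, and a split of existing output. Protocol version is already among the listed subject data (SAP 10.1), and no new data are required.
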